#### 7.1.2. Patient characteristic balancing

[figure not shown]
In this study, matched cohorts (warfarin cohort versus apixaban cohort) will be created. A propensity score will be calculated based on multivariable logistic regressions in order to account for confounding effects\* and to ensure that patient characteristics will be balanced between the warfarin cohort and apixaban cohort. An inverse probability of treatment weighting (IPTW) method using the calculated propensity score will be applied. To avoid sample size inflation and to ensure appropriate estimation of variances, s-IPTW (stabilized IPTW) is used here.

Balanced (after IPTW) patient clinical and demographic characteristics will be shown. Covariate balance between apixaban and warfarin cohorts after s-IPTW will be assessed in terms of the standardized differences with a threshold of 0.1. We will present the data for each variables and standardized differences in the same table side by side to ensure that two cohorts are balanced after IPTW.

\* Covariates used for the calculation of propensity score

- Gender: male or female
- Age: absolute years
- BMI: categories BMI (kg/m^2) (<18, 18 to <22, 22 to <25, 25+, missing)
- CHADS2 score: absolute score, categories (0, 1, 2, 3, 4, 5, 6)

PFIZER CONFIDENTIAL

[figure not shown]

- CHA2DS2-VASc: absolute score, categories (0, 1, 2, 3, 4, 5, 6, 7, 8, 9)
- Treatment status of the most recent stroke before the index date (outpatient treatment, inpatient treatment, missing)
- mRS (modified Rankin Scale) at time of admission due to most recent stroke (0,1,2,3,4,5, missing)
- JCS (Japan coma scale) at time of admission due to most recent stroke (I, II, III, missing)
- ADL (Activities of daily living) at time of admission due to most recent stroke (0-19, 20-39, 40-59, 60-79, 80-100, missing)
- Duration of hospitalization due to most recent stroke
- Destination after discharge from hospitalization due to most recent stroke (1 or 5 or other (2,3,4,6,7,8,9))
- Use of tPA or urokinase for treatment of most recent ischemic stroke (thrombolytic therapy)
- Type of most recent stroke stroke (TIA, ischemic stroke, cerebral bleeding, cardiogenic thromboembolism, unknown/others)
- 

*Note: in patients with a medical history of incidence multiple stroke events, only information regarding most recent stroke (i.e., stroke event closest to the index date) will be used.*

- Comorbidities
  - Hypertension
  - Heart failure in baseline
  - Coronary heart disease in baseline
  - Peripheral arterial disorder in baseline
  - History of myocardial infarction
  - Hyperthyroidism or thyrotoxicosis in baseline
  - Diabetes in baseline
  - Liver diseases in baseline
  - Diabetes mellitus diagnosis in baseline
  - Cancer diagnosis in baseline
  - Dementia in baseline
  - Renal diseases in baseline
  - Gastrointestinal ulcer in baseline

PFIZER CONFIDENTIAL

- History of bleeding
- Medicines
  - Treated with antiplatelet drug in baseline
  - Treated with NSAIDs in baseline
  - Treated with anti-hypertensives in baseline
  - Treated with anti-arrhythmics in baseline
  - Treated with beta-blockers in baseline
  - Treated with heparins in baseline
- Others
  - Cardioversion
  - Cardiac ablation

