De-identified health claim data from 458 acute-care hospitals across Japan (as of Dec.22, 2021) available from the MDV (Tokyo, Japan, MDV) database. In brief, the MDV database comprises administrative data pertaining to approximately 38 million individuals managed in the inpatient and outpatient settings. Each patient is associated with a specific ID to which all inpatient and outpatient data are linked.

Study size :

In this study, eligible patients will be aggregated backward.

- The number of estimated patients;
- All registered patients: approximately 38 millions (2008-2021)
- Patients with ischemic stroke: 1.2 millions
- Patients with TIA: 98,887
- Patients with atrial fibrillation: 1.3 millions
- AF patients with a history of ischemic stroke: 226,000
- AF patients on warfarin: 251,000
- AF patients on apixaban: 237,000
- The number of patients who experienced recurrent ischemic stroke on warfarin or apixaban: unknown

Data analysis :

The detailed methodology for data analysis will be described in the Statistical Analysis Plan (SAP). Briefly,

As a first step, extracted patients will be divided into two cohorts, primary prevention cohort and secondary prevention cohort based on the previous diagnosis of stroke. Clinical and demographic characteristics will be compared with two cohorts at baseline and on the index date (date of the initiation of warfarin and apixaban) and incidence rates of stroke/SE and major bleeding per 1,000 person-years will be calculated during follow-up period. In addition, interaction analysis will be conducted to investigate an interaction between OAC (warfarin/apixaban) and presence or absence of the previous episode of stroke.

- As a second step, only secondary prevention cohort will be used for further analyses as follows, Crude (before IPTW) patient characteristics will be compared between warfarin and apixaban cohorts using appropriate methods (continuous variables: unpaired t-test or Mann-Whitney U-test, categorical variables: chi-square test)
- A propensity score will be calculated based on multinomial logistic regressions in order to account for confounding effects and to ensure that patient characteristics will be balanced between the warfarin cohort and apixaban cohort. An inverse probability of treatment weighting (IPTW) method using the calculated propensity score will be applied. To avoid sample size inflation and to ensure appropriate estimation of variances, s-IPTW (stabilized IPTW) will be used here.

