7. RESEARCH QUESTION AND OBJECTIVES

The pivotal randomized clinical trial, ARISTOTLE study, and other RWE, in which medical and claims data have been retrospectively analyzed, have shown that the risks of incidence of stroke + systemic embolism and major bleeding in patients with NVAF treated with apixaban is equal to or lessor than those in patients treated with warfarin. As mentioned above, patients with NVAF and with a history of ischemic stroke (that is, in secondary prevention) could be at higher risk of recurrence and bleeding. Although neurologists generally use direct oral anticoagulants (DOAC) for secondary prevention, a significant portion of the patients in secondary prevention are still treated with warfarin in Japan. There is no clear evidence that apixaban is superior to warfarin in reducing the risk of recurrence or bleeding in Japanese patients with secondary prevention of

stroke. The research question of this study is whether apixaban is associated with lower risk of stroke (ischemic stroke and hemorrhagic stroke) and bleeding compared to warfarin in higher-risk secondary prevention patients as well.

7.1. Primary objective:

The effectiveness of study in secondary prevention cohort will be conducted to elucidate the following,

1. Incidence rate (per 1,000 person-years) of a composite of recurrent stroke (ischemic stroke and hemorrhage stroke) in NVAF patients treated with warfarin or apixaban.
2. Time course of proportion of a composite of the incidence of recurrent stroke (ischemic stroke and hemorrhage stroke) -free NVAF patients treated with warfarin or apixaban (shown as two Kaplan-Meier curves, for warfarin cohort and apixaban cohort, which will be statistically compared by a Log-rank test).
3. Risk of a composite of recurrent “Ischemic stroke” (“cardiogenic cerebral embolism” + “cerebral infarction”) and hemorrhagic stroke and SE in patients treated with apixaban compared to that in patients treated with warfarin (Hazard ratio and 95% confident intervals will be calculated by a COX proportional hazard method) (**primary effectiveness analysis**).

* TIA is not included in endpoints.

The safety of study will be conducted to elucidate the following,

1. Incidence rate of recurrent bleeding, such as major bleeding, intracranial hemorrhage, gastrointestinal tract bleeding or intraocular bleeding in NVAF patients treated with warfarin or apixaban

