8.7. Data analysis

The detailed methodology for data analysis will be described in the Statistical Analysis Plan (SAP).

As a first step, extracted patients will be divided into two cohorts, primary prevention cohort and secondary prevention cohort based on the previous diagnosis of stroke. Clinical and demographic characteristics will be compared with two cohorts at baseline and on the index date (date of the initiation of warfarin and apixaban) and incidence rates of stroke/SE and major bleeding per 1,000 person-years will be calculated during follow-up period. In addition, interaction analysis will be conducted to investigate an interaction between OAC (warfarin/apixaban) and presence or absence of the previous episode of stroke.

- As a second step, only secondary prevention cohort will be used for further analyses as follows, Crude (before IPTW) patient characteristics are compared between warfarin and apixaban cohorts using appropriate methods (continuous variables: unpaired t-test or Mann-Whitney U-test, categorical variables: chi-square test)
- A propensity score is calculated based on multinomial logistic regressions in order to account for confounding effects and to ensure that patient characteristics are balanced between the warfarin cohort and apixaban cohort. An inverse probability of treatment weighting (IPTW) method using the calculated propensity score will be applied. To avoid sample size inflation and to ensure appropriate estimation of variances, s-IPTW (stabilized IPTW) is used here.
- Balanced (after IPTW) patient clinical and demographic characteristics are shown. Covariate balance between apixaban and warfarin cohorts after s-IPTW is assessed in terms of the standardized differences with a threshold of 0.1
- Kaplan Meier curves of balanced cohorts for each endpoint are drawn.
- Incidence rates of endpoints are calculated and shown per 1000 person-years.
- Hazard ratios with 95% confidence intervals will be calculated using a Cox proportional hazards regression model that incorporate only the index OACs as independent variables.

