8.8. Quality control

This study is a retrospective analytical study using quality-controlled data in a pre-existing database, and primary data collection will not be conducted. As for the data provided, quality of the data is guaranteed by MDV Co. Ltd., which has professional teams specialized in the maintenance and improvement of data quality. All these processes are consistently managed in-house. All of operations for data management in MDV Co. Ltd. are conducted in accordance with standard operational procedures of MDV Co. Ltd. For quality assurance of analysis, the vendor

which deals with the analysis will conduct code review of all modules of program, descriptive statistics review of all variables and patients row data examination of all output results in a test phase.

Statistical analysis will be also outsourced to a specialist (a vendor specialized to the statistics). Validity of analysis programs and the obtained results will be confirmed by the vendor according to the internal standard of procedures.

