## 5. ENDPOINTS AND COVARIATES

### 5.1. EFFICACY/EFFECTIVENESS ENDPOINT(S)

#### 5.1.1. Primary effectiveness endpoint and primary analyses

The following outcomes will be assessed as effectiveness endpoints. Primary endpoint is incidence of a composite of recurrent stroke (ischemic and hemorrhagic stroke)/SE in NVAF patients treated with warfarin or apixaban. The definition of “recurrent” is as follows, “once patients discharge from the hospital and become outpatients and then rehospitalized due to stroke (major reason for the hospitalization is stroke described in the DPC admission information)

[figure not shown]
[figure not shown]
1. Incidence rate (per 1,000 person-years) of a composite of recurrent stroke (ischemic and hemorrhagic stroke)/SE during the follow-up period in NVAF patients treated with warfarin or apixaban
2. Time course of proportion of the incidence of a composite of recurrent stroke (ischemic and hemorrhagic stroke)/SE-free NVAF patients treated with warfarin or apixaban (shown as two Kaplan-Meier curves, for warfarin cohort and apixaban cohort, which will be statistically compared by a Log-rank test).
3. Risk of a composite of recurrent stroke (ischemic and hemorrhagic stroke)/SE in patients treated with apixaban compared to that in patients treated with warfarin. Hazard ratio and 95% confident intervals will be calculated by a COX proportional hazard method

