## 7.2. STATISTICAL ANALYSES

- SAS software version 9.4 (SAS Institute Inc. NC, USA) will be used for the analysis.
- For primary effectiveness analysis and primary safety analysis (see 5.1 and 5.2), statistical tests will be performed at  $p=0.05$  (two-sided) with no adjustment for multiplicity. P values less than 0.05 will be regarded as statistically significant.
- We will conduct multiple secondary analysis as shown below and these repetitive statistical analyses may cause the "Multiple Testing Problem". Here these multiple analyses will be concluded only as an exploratory purpose and we do not intend to conclude anything from the results obtained from sub-endpoint analyses here. No multiple testing adjustment will be taken.

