### 7.2.1. Sensitivity analysis

E-values (evidence for causality) will be calculated for the primary effectiveness and safety analysis from calculated hazard ratios and 95% confident intervals to estimate the extent of unmeasured confounding. In this study, the E-value is defined as the minimum strength of association on the calculated hazard ratio and the limit of the confidence interval closest to the null in the primary effectiveness and safety analysis.

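### The plan relies on stabilised weights for correct variances and names no robust variance for the weighted Cox model or log-rank test

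*SAP*

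**What the plan says.** SAP 7.1.2 balances the warfarin and apixaban cohorts by stabilised inverse probability of treatment weighting and explains the choice in one sentence: "To avoid sample size inflation and to ensure appropriate estimation of variances, s-IPTW (stabilized IPTW) is used here". The protocol abstract has the same statement, "To avoid sample size inflation and to ensure appropriate estimation of variances, s-IPTW (stabilized IPTW) will be used here", and so does protocol 8.7.

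The analyses on the weighted cohorts are then named without a variance estimator:

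- Protocol 8.7 specifies a "Cox proportional hazards regression model that incorporate only the index OACs as independent variables".
- Protocol 7.1 says of the primary effectiveness and primary safety analyses that "Hazard ratio and 95% confident intervals will be calculated by a COX proportional hazard method".
- SAP 5.1.1 says the Kaplan-Meier curves are "statistically compared by a Log-rank test"; SAP 5.2.1 says the same for major bleeding.
- SAP 7.2 sets the decision rule for the primary analyses: "P values less than 0.05 will be regarded as statistically significant".
- SAP 7.2.1 applies the E-value to the hazard ratio and to "the limit of the confidence interval closest to the null in the primary effectiveness and safety analysis".

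The summary table in SAP 7.2.3 adds only the model's name. SAP Appendix 2, the place for further statistical methodology, is marked as not applicable. SAP 7.2 fixes the software as SAS 9.4 but not the variance option.

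**The concern.** Stabilised weights average about 1, so the weighted number of patients stays close to the real number. That deals with one source of false precision. It does not deal with a second: some patients count for much more than one person and others for less. The inverse-information standard error from a weighted Cox model treats each weight as a count of independent patients and so ignores this spread. The same holds for a log-rank test computed from weighted counts with its ordinary variance.

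A programmer who follows the text and fits a weighted Cox model in SAS without a further option gets the model-based error. Every primary inferential result depends on it: two hazard ratios with intervals, two tests at 0.05, and two E-values for the limit nearest the null. An understated standard error pushes all of them towards a finding of difference. The propensity model in SAP 7.1.2 has more than 30 covariates, many of them categorical, and no weight truncation is stated, so near-uniform weights cannot be taken for granted.

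**Working it through.** The plan gives no figure for weight spread or for the standard error, so there is none to reproduce. The calculation shows what a model-based error would do under assumed weight spreads.

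**Inputs from the documents.** Two-sided alpha 0.05; expected hazard ratio 0.65; lowest control rate 1.2% per year; more than 15,000 secondary prevention patients (all SAP 7.2 and 7.2.2); follow-up capped at 2 years (protocol 8.1.1.7).

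**Assumptions.** Weight CVs of 0.15, 0.30, 0.455 and 0.56; a 1:1 split; exponential discontinuation with a median of 2 years.

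**Step 1: approximation.** With weights unrelated to outcome, the true variance is about (1 + CV²) times the model-based one. Effective sample size is 1/(1 + CV²) of the actual number, and actual type I error is 2Φ(−1.96/√(1 + CV²)). At CV 0.30: 1/1.09 = 92%, and 2Φ(−1.96/1.044) = 6.0%.

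**Step 2: simulation.** n = 6,000; four standard normal covariates affecting treatment and outcome (log hazard ratio 0.27 each); true treatment hazard ratio 1; estimated logistic propensity score; stabilised weights; follow-up as above; mean 165 events; 8,000 runs per setting (Monte Carlo error 0.24-0.33 points).

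| Weight CV | Effective sample size | Type I, approximation | Type I, model-based | Type I, sandwich | Sandwich SE / model SE (k) |
|---|---|---|---|---|---|
| 0.15 | 98% | 5.3% | 5.5% | 5.2% | 1.014 |
| 0.30 | 92% | 6.0% | 6.7% | 5.4% | 1.055 |
| 0.455 | 83% | 7.4% | 8.4% | 5.4% | 1.121 |
| 0.56 | 76% | 8.7% | 9.5% | 5.1% | 1.174 |

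The empirical standard deviation of the log hazard ratio was 1.019, 1.065, 1.136 and 1.189 times the model-based error, so the sandwich captures most of the gap.

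**Step 3: does the result depend on the simulation design?** A second simulation (n = 15,000, 600 runs per setting) gave, model-based against sandwich, 4.8% against 4.8% with no treatment selection, 7.5% against 4.5% at an effective sample size of 93%, and 14% against 5% at 71%. The direction is the same; the size depends on the design. In its most extreme setting (42%) the sandwich itself rejected 8% of the time, so it is not exact when weights are very uneven.

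**Step 4: effect on a result at the expected hazard ratio.** With 7,500 per arm, hazards h of 0.012 and 0.65 × 0.012 = 0.0078 per year, and discontinuation hazard ln 2/2 = 0.3466, expected events per arm are 7,500 × h/(h + 0.3466) × (1 − e^(−2(h + 0.3466))). This gives 128.5 + 83.8 = 212. The model-based SE is 2/√212 = 0.1374. The upper limit is 0.65 × exp(1.96 × 0.1374 × k). With R = 1/upper limit, the E-value is R + √(R(R − 1)). The largest hazard ratio declared significant is exp(−1.96 × 0.1374 × k).

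| k | Upper 95% limit | E-value of that limit | Largest significant hazard ratio |
|---|---|---|---|
| 1 (model-based) | 0.851 | 1.63 | 0.764 |
| 1.014 | 0.854 | 1.62 | 0.761 |
| 1.055 | 0.864 | 1.59 | 0.753 |
| 1.121 | 0.879 | 1.53 | 0.739 |
| 1.174 | 0.892 | 1.49 | 0.729 |

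The conclusion at 0.65 holds throughout. An estimate between about 0.73 and 0.76 would change from significant to not significant at the largest assumed spread.

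**The case against.** The strongest reply is that the sentence explains why stabilised rather than raw weights are used, and on that it is right. Raw weights in two equal arms roughly double the weighted number, so a model-based error would be too small by about √2, and even with near-uniform weights type I error would be 2Φ(−1.96/1.414) = 16.6%. Stabilisation removes that error. This stands: a reader might infer that the statement on variances is simply false, but it is incomplete, and incomplete only to the extent that the weights vary.

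A reader might also infer that the sponsor has chosen a model-based error. The documents do not say so. Protocol 8.8 states that "Validity of analysis programs and the obtained results will be confirmed by the vendor", under internal procedures not reproduced there, and those procedures might call for a robust variance. This too stands, but validation after the fact does not pre-specify an estimator.

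The weight spreads are assumptions and the two simulations differ in size, so no error rate above is a property of this study. That also stands.

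Finally, a reader might extend the point to the power statement in SAP 7.2.2. The documents do not support this. All 12 sample sizes reproduce within 1.2% with two years of follow-up, they are given per group, and the SAP words its conclusion only as a probability. No shortfall in power is shown.

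**Conclusion.** The point holds as an omission that should be corrected. The plan offers stabilisation as its only variance provision for the weighted analyses, and stabilisation does not account for unequal weights. If the default model-based error is used, type I error is close to nominal at a weight CV of about 0.15 and about 6-9% at 0.3-0.55; these figures are illustrative and rest on the assumed spreads and the simulation design. At the SAP's expected hazard ratio of 0.65, with 212 events under the follow-up assumptions shown, the upper limit moves from 0.851 to at most 0.892 and the E-value of that limit from 1.63 to 1.49. Significance is unchanged. The omission therefore matters for a borderline estimate, and because an estimator left open can be chosen after the results are seen.

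**What to change.** In SAP 7.1.2, and in the matching sentences of the protocol abstract and protocol 8.7, replace the statement with two: stabilised weights are used to keep the weighted number of patients near the actual number; and all weighted Cox hazard ratios, 95% confidence intervals and p-values use a robust sandwich variance (PROC PHREG with WEIGHT, COVS(AGGREGATE) and patient ID).

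In SAP 5.1 and 5.2, take the p-value for the Kaplan-Meier comparison from that model, which avoids programming a separate robust weighted log-rank test. In SAP 7.2.1, compute the E-value from the robust interval. Report the weight CV or effective sample size beside the balance table; because the sandwich treats the propensity score as known and is not exact, readers need this to judge the intervals.

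The cost is one SAS option and a few reworded sentences. Intervals become about 1%, 6%, 12% or 17% wider on the log scale at weight CVs of 0.15, 0.30, 0.455 or 0.56. No further data are needed.

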### 4. ANALYSIS SETS/POPULATIONS

#### 4.1. FULL ANALYSIS SET

##### 4.1.1. Inclusion criteria

*Patients must meet all the following selection criteria*

1. *Patients registered in the MDV database 2008 through 2021.*
2. *Patients newly diagnosed with non-valvular atrial fibrillation*
3. *Patients who started anticoagulation treatment with either warfarin or apixaban after diagnosis of NVAF*
4. *Age 20 years or older on the index date*
5. *Patients who have a history\* of stroke (cerebral infarction, cardioembolic stroke, or hemorrhagic stroke) or TIA before the index date are inclusion criteria only for secondary prevention cohort, otherwise patients will be included in the primary prevention cohort.*

\* A history of stroke is checked as far back as possible from the INDEX DATE to see if there is a history of stroke. That is, the period is from the date each patient first appeared in the MDV database to the day before the index date.

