### 5.4. COVARIATES

Variable	Role	Operational definition
Previous stroke		
Previous incidence of stroke	Patient characteristic:	
Previous incidence of TIA	Patient characteristic:	Defined elsewhere using ICD-10 codes

PFIZER CONFIDENTIAL

Types of previous stroke	Patient characteristic:	cardioembolic stroke or cerebral infarction
Treatment status	Patient characteristic:	Inpatients or outpatients
Hospitalization days	Patient characteristic:	0 or days in hospital
NVAF diagnosis and treatment		
Year	Patient characteristic	Year first diagnosed with NVAF
Anticoagulant	Patient characteristic	Warfarin or apixaban
Patients		
age	Patient characteristics on index date	Years
Age category	Patient characteristics on index date	
age $\leq 65$		
age $65 < , \leq 75$		
age $75 <$		
Gender category	Patient characteristics on index date	Male or female
Body weight	Baseline characteristic	Kg (if available)
Height	Baseline characteristic	cm (if available)
BMI	Baseline characteristic	Calculated from body weight and height using a formula of (weight [kg]) / (height [m]) 
Comorbidity profile		
Chronic obstructive pulmonary disease (COPD)	Baseline characteristic	Defined elsewhere using ICD-10 codes
Congestive heart disease	Baseline characteristic	Defined elsewhere using ICD-10 codes
Ischemic heart/coronary artery disease	Baseline characteristic	Defined elsewhere using ICD-10 codes
Diabetes	Baseline characteristic	Defined elsewhere using ICD-10 codes
Hyperlipidemia	Baseline characteristic	Defined elsewhere using ICD-10 codes
Hypertension	Baseline characteristic	Defined elsewhere using ICD-10 codes
Liver disease	Baseline characteristic	Defined elsewhere using ICD-10 codes
Renal disease	Baseline characteristic	Defined elsewhere using ICD-10 codes
Peripheral vascular disease	Baseline characteristic	Defined elsewhere using ICD-10 codes
Pregnancy	Exclusion criteria	Presence of "pregnancy"-related ICD-10 codes.

PFIZER CONFIDENTIAL

Cancer	Baseline characteristic	Defined elsewhere using ICD-10 codes
VTE	Baseline characteristic (exclusion criteria)	Defined elsewhere using ICD-10 codes
Medicines		
Anti-hypertensive drugs	Baseline characteristic	Defined elsewhere using drug codes
Anti-platelet drugs	Baseline characteristic	Defined elsewhere using drug codes
NSAIDs (chronic use*)	Baseline characteristic	Defined elsewhere using drug codes
Statins	Baseline characteristic	Defined elsewhere using drug codes
Outcomes		

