## 7. STATISTICAL METHODOLOGY AND STATISTICAL ANALYSES

### 7.1. STATISTICAL METHODS

#### 7.1.1. Patient characteristics

Patients characteristic will be compared between two groups before and after IPTW. Means, medians, and standard deviations will be provided for continuous variables when performing descriptive analysis of continuous data. Numbers and percentages will be provided for dichotomous and polychotomous variables when performing descriptive analysis of categorical data. Bivariate comparisons of baseline characteristics and outcomes measures will be provided. Appropriate tests (unpaired t-test or Mann-Whitney U-test, categorical variables: chi-square test) will be used based on the distribution of the measure. The balance of these covariates between cohorts will be assessed using the standardized difference (cutoff: 0.1)

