### 7.2.3. Summary of Analyses

All analysis other than patient characteristics will be conducted as a two-sided p-value less than 0.05.

Patient characteristics will be compared using standardized difference as a cut-off value of 0.1.

Outcome/items to be examined	Analysis Cohort	Supports Protocol Objective Number	Subgroup	Statistical Method	Covariates/Strata	Missing Data

PFIZER CONFIDENTIAL

Patients characteristics	Cohorts in Step 1 and Step 2		None	unpaired t-test or Mann-Whitney U-test, categorical variables: chi-square test		No imputation
The incidence rates of stroke/SE and major bleeding per 1,000 person-years	Cohorts in Step 1 and Step 2		None	1000 person-years	Refer to section 5.4	No imputation
Interaction analysis	Cohorts in Step 1 and Step 2		None	Cox proportional hazards regression model	Warfarin/apixaban, primary/secondary	No imputation
Incidence rate of a composite of recurrent stroke (ischemic and hemorrhagic)/SE (primary effectiveness analysis)	Balanced cohorts	Effectiveness 1	None	1000 person-years	Refer to section 5.4	No imputation
Incidence of cardiogenic cerebral embolism (secondary effectiveness endpoint)	Balanced cohorts	Effectiveness 1	None	1000 person-years	Refer to section 5.4	No imputation
Incidence of cerebral infarction (secondary effectiveness endpoint)	Balanced cohorts	Effectiveness 1	None	1000 person-years	Refer to section 5.4	No imputation
Incidence rate of major bleeding (primary safety endpoint)	Balanced cohorts	Safety 1	None	1000 person-years	Refer to section 5.4	No imputation
Incidence rate of intracranial hemorrhage (secondary safety endpoint)	Balanced cohorts	Safety 1	None	1000 person-years	Refer to section 5.4	No imputation
Incidence rate of gastrointestinal bleeding (secondary safety endpoint)	Balanced cohorts	Safety 1	None	1000 person-years	Refer to section 5.4	No imputation
Incidence of rate of intraocular bleeding (secondary safety endpoint)	Balanced cohorts	Safety 1	None	1000 person-years	Refer to section 5.4	No imputation
Time course of proportion of a composite of the incidence of recurrent stroke (ischemic and hemorrhagic)/SE -free NVAF patients treated with warfarin or apixaban	Balanced cohorts	Effectiveness 2	None	Kaplan Meier curves	Refer to section 5.4	No imputation

PFIZER CONFIDENTIAL

Time course of proportion recurrent cardiogenic cerebral embolism-free NVAF patients treated with warfarin or apixaban	Balanced cohorts	Effectivess 2	None	Kaplan Meier curves	Refer to section 5.4	No imputation

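### Calendar year is collected but absent from the readable propensity-score list for starters pooled over 2008-2021, so both primary hazard ratios are open to confounding by calendar period.

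*SAP*

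**What the plan says.** SAP 4.1.1 admits "Patients registered in the MDV database 2008 through 2021", and SAP 2.1.3 assigns cohorts by the first anticoagulant after NVAF diagnosis, with no calendar limit. SAP 5.4 collects "Year first diagnosed with NVAF" as a patient characteristic, and the index date supplies the index year.

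The list headed "Covariates used for the calculation of propensity score" in SAP 7.1.2 covers sex, age, BMI, the two stroke-risk scores, details of the most recent stroke, comorbidities, medicines, cardioversion and ablation. It shows no calendar term.

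Protocol 8.7 specifies a "Cox proportional hazards regression model that incorporate only the index OACs as independent variables", so all adjustment comes from the weights. SAP 4.4 plans no subgroups. SAP 7.2.1 offers one sensitivity analysis: "E-values (evidence for causality) will be calculated for the primary effectiveness and safety analysis". SAP 7.1.1 and 7.1.2 judge balance by a standardized difference of 0.1 and state no action if it is exceeded.

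**The concern.** Calendar period confounds the comparison if two things hold: the drugs' start years differ, and stroke risk, bleeding risk, coding or patient mix changed over the window in ways the listed covariates do not capture. Two points in the documents make this plausible without proving it.

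- For stroke history, SAP 4.1.1 says "the period is from the date each patient first appeared in the MDV database to the day before the index date". With data from 2008, a 2009 starter has at most about 2 years of look-back and a 2021 starter up to about 14. The prior strokes that define the cohort can therefore be older in later starters.
- The protocol's reference list dates the pivotal apixaban trial to 2011, three years into the window. The earliest years therefore probably hold few or no apixaban starters. This is an assumption, because the documents do not give the date of first apixaban use.

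The same weighted cohorts feed the primary effectiveness and the primary safety hazard ratio, each tested at two-sided 0.05. An adjustment for year chosen after results are seen would be post hoc.

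**Working it through.** **Inputs.** From the documents: window 2008-2021 (SAP 4.1.1); balance limit 0.1 (SAP 7.1.1); hazard ratio 0.65, control rates 1.2 to 2.6%/year and more than 15,000 patients (SAP 7.2.2); follow-up of at most two years, ending earlier at discontinuation or switch (Protocol 8.1.1.7). Assumed: apixaban starts from 2012, true hazard ratio 1.00, and no part of the trend absorbed by other covariates. Let t = 1 to 14 for 2008 to 2021.

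**Scenarios.** (i) Each drug's starts grow in proportion to t. (ii) Each drug's starts are flat. (iii) Total starts grow in proportion to t, and the apixaban share rises by 5 points a year from 5% in 2012 to 50% in 2021.

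**Imbalance in index year.** The standardized difference is the gap in means divided by the square root of the mean of the two variances. In (ii), warfarin has mean 2014.5 and variance (14² − 1)/12 = 16.25; apixaban has mean 2016.5 and variance (10² − 1)/12 = 8.25. This gives 2.0/√12.25 = 0.57.

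**Apparent hazard ratio.** This is the mean of (1+g)^year over apixaban starts divided by the same mean over warfarin starts. In (ii) with g = −5%: [0.95⁴(1 − 0.95¹⁰)/10] / [(1 − 0.95¹⁴)/14] = 0.89.

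| Scenario | Gap, years | Std. difference | HR at −5%, +5% per year | HR at −2%, +2% per year |
|---|---|---|---|---|
| (i) | 0.70 | 0.23 | 0.96, 1.03 | 0.98, 1.01 |
| (ii) | 2.00 | 0.57 | 0.89, 1.09 | 0.96, 1.04 |
| (iii) | 2.64 | 0.90 | 0.87, 1.13 | 0.95, 1.05 |

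A gap of about 0.3 years already reaches the 0.1 limit. With a first apixaban year anywhere from 2011 to 2013, the standardized difference spans 0.14 to 1.01 and the apparent hazard ratio at 5% spans 0.85 to 1.14. If half of a 5% trend is absorbed (2.5% left), scenario (iii) gives 0.93 to 1.07.

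**The plan's sample sizes.** Events D = 4(1.960 + 0.842)²/(ln HR)², divided by the sum of the two arms' two-year event probabilities. For HR 0.6 and 1.2%/year: 120.3/(0.0237 + 0.0143), which is 3,166 per group before rounding of the displayed terms, against 3,166 stated. All twelve cells agree within about 1.2%.

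**Cost of restricting to 2012-2021 and weighting on year.** Early warfarin starters lost: (i) 10/105 = 10%; (ii) 4/14 = 29%; (iii) 10/74.75 = 13%. In (iii) apixaban makes up 30.25/105 = 28.8% of starters, so 15,000 patients split 10,679 warfarin to 4,321 apixaban. Of these, 9,250 warfarin starters are retained. The largest stabilized weight is [4,321/(4,321 + 9,250)]/0.05 = 6.4. Effective samples are 8,891 warfarin (96% of those retained) and 2,969 apixaban (69%).

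Power is Φ(|ln 0.65|·√(D·p(1−p)) − 1.96), with p the warfarin share of the (effective) sample. For (iii) at 1.2%/year over two years:

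- Before: D = 320.1, p = 0.712, z = 1.53, power 0.94.
- After: D = 256.8, p = 0.750, z = 1.03, power 0.85.

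With equal arms of 7,500, which (i) and (ii) permit, power goes from 0.96 to 0.95 in (i) and to 0.91 in (ii). With only one year on treatment (assumed), (iii) goes from 0.70 to 0.56 at 1.2%/year, and is 0.88 after the change at 2.6%/year.

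**The case against.** The strongest reply is that every input driving the size is assumed: uptake, first apixaban year and trend. That stands. The only document counts, 251,000 AF patients on warfarin and 237,000 on apixaban, are near equal, while scenario (iii) implies 28.8% apixaban. Those counts cover all AF users and not new secondary-prevention starters, so they neither support nor refute a shift. The details of the most recent stroke in the propensity score may also absorb part of the look-back effect.

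Second, year may appear in the balance table through SAP 5.4. It may, but no response to imbalance is stated.

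Third, SAP 7.2.3 writes "Refer to section 5.4" under covariates for the Cox rows, and 5.4 lists year. That section also lists the exposure and the outcomes, so it cannot be a model specification, and such a reading would contradict Protocol 8.7. The wording needs its own clarification.

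Fourth, the list in SAP 7.1.2 has an empty bullet and figures that are not shown. A year term there is possible but unlikely, since the bullet sits among stroke items; hence "readable" in the heading.

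A reader might also take the two hospital counts, 450 in June 2021 and 458 in December 2021, as evidence of changing patient mix. They are six months apart at the end of the window and carry almost no weight.

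**Conclusion.** The concern holds as an exposure to bias, and the plan should be changed. A measured, available baseline variable is left out of the only adjustment behind both primary hazard ratios, and no other planned analysis compensates. An E-value adjusts for nothing.

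A reader might infer that the hazard ratios are biased, or biased in apixaban's favour. The documents do not support that: the sign depends on an unknown trend, and there is no bias if risk, coding and patient mix were stable or start years did not differ. Nor would the expected 0.65 disappear. In scenario (iii) at 5% per year, an observed 0.65 would correspond to 0.65/1.128 = 0.58 or 0.65/0.865 = 0.75, which is shifted but in the same direction. All sizes rest on the assumed uptake and trends.

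**What to change.** 1. Add index year (categorical or spline) to the propensity score and the balance table. Use the index year; 5.4 names only the diagnosis year.
2. State the action if its standardized difference exceeds 0.1 after weighting, for example stratifying the weighted Cox model by index year.
3. For positivity, limit the Step 2 comparison to index years in which both drugs have starters, fixed from treatment counts before outcomes are examined. Restriction alone is not enough: in (iii) it leaves a gap of 1.7 years, a standardized difference of 0.69 and apparent hazard ratios of 0.91 to 1.08 at 5% per year.
4. Report the all-years analysis without year as a prespecified sensitivity analysis, since year may predict treatment strongly and outcome only weakly.

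The dates are already available. Items 1, 2 and 4 are SAP edits; item 3 also needs a matching protocol note, because registration from 2008 through 2021 is a protocol inclusion criterion. The price is the loss of 10% to 29% of warfarin starters in the assumed scenarios, more variable weights, and the lower power shown above, largest where drug use shifted most. Adjusting for year may also slightly amplify residual confounding, which Protocol 8.9 concedes cannot be fully excluded.
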